### 9. **EFFICACY ANALYSIS**

## 9.1. Primary Efficacy Endpoint

The primary efficacy endpoint is the ARR at the end of Month 24.

### 9.1.1. Primary Analysis

Definition of relapses

The relapse rate will be based on only relapses that were confirmed by the treating investigator to meet the protocol-defined definition of relapse, based on the EDSS scores obtained by the blinded evaluator (Section 9.1.2.3 in the protocol). New or recurrent

neurological symptoms that occur less than 30 days following the onset of a protocol-defined relapse will be considered part of the same relapse, i.e., if 2 relapses have onset days that are <30 days of one another, they will be counted as 1 relapse with onset date as the earlier of the 2 relapses.

### Definition of relapse rate

The relapse rate for each treatment group will be calculated as the total number of relapses experienced in the group divided by the total number of days in the study for the group, and multiplied by 365.25. This is called the unadjusted relapse rate and it will be reported for each treatment group.

The relapse rate for each patient will be calculated as the number of relapses for an individual patient divided by the number of days that patient participated in the study, and multiplied by 365.25. Summary statistics of the individual relapse rate for each treatment group will be reported.

Primary Analysis method – annualized relapse rate

All relapses will be identified as confirmed or unconfirmed prior to database lock. The primary analysis of ARR will be performed using a Poisson regression model. The model will compare treatment groups, adjusted for region, age at Baseline, and the Baseline number of GdE lesions, and will include the natural log transformation of time on study as an offset term. The adjusted relapse rates and their associated 95% CIs, the rate ratios and their associated 95% CIs, and p-values will be reported.

The primary analysis will be repeated in each of the pre-specified subgroups shown in section 5. Forest plots showing the rate ratios and 95% CI for the overall result and the results in each subgroup will be constructed.

Relapse results will be listed.

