#### Part B

The primary analysis for the ARR will be carried out using a Poisson regression model. The model will compare treatment groups, adjusted for region, age, and the number of GdE lesions at baseline. To account for multiple comparisons, each of the 2 treatment comparisons with IFN  $\beta$ -1a will be tested at the alpha = 0.025 level. Results will be summarized by randomized treatment group and expressed as unadjusted and adjusted relapse rates, odds ratios, corresponding 95% confidence intervals, and p-values.

The relapse rate will be based on only those relapses that were determined by the treating investigator to meet the protocol-defined definition of relapse, based on the EDSS scores obtained by the blinded evaluator (Section 9.1.2.3). New or recurrent neurological symptoms that occur less than 30 days following the onset of a protocol-defined relapse will be considered part of the same relapse, i.e., if 2 relapses have onset days that are  $\leq$ 30 days of one another, they will be counted as 1 relapse (see Section 9.1.2.3).

The relapse rate for each treatment group will be calculated as:

(total relapses in the arm) / (total days in the study for the arm) \* 365.25

The 3 key secondary endpoints will be tested in order in the RPC1063 1 mg dose above the RPC1063 0.5 mg dose. If both doses are significant on the primary endpoint, then the first comparison on the key secondary endpoints will be between the RPC1063 1 mg group and the IFN  $\beta$ -1a group at the 5% level of significance. If that comparison is successful, then the same endpoint will be tested for the RPC1063 0.5 mg group vs. the IFN  $\beta$ -1a group comparison at the 5% level of significance. This procedure will continue down the key secondary endpoint list until a comparison fails to reach statistical significance,

the primary endpoint, then the will be employed on the surviving dose only, at the 2.5% level of significance for each key secondary endpoint.

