### 5. GENERAL STATISTICAL CONSIDERATIONS

Statistical testing for the primary efficacy endpoint will be made between each RPC1063 group and the IFN  $\beta$ -1a group (2 treatment contrasts). To account for multiple comparisons, each of the 2 treatment comparisons will be tested at the alpha = 0.025 level.

To control for type 1 error, the 3 key secondary endpoints will be tested in order in a sequential, that ranks the RPC1063 1 mg dose above the RPC1063 0.5 mg dose and the key secondary endpoints in the order shown in section 4.2. If both doses are significant on the primary endpoint, then the first comparison on the key secondary endpoints will be between the RPC1063 1 mg group and the IFN  $\beta$ -1a group at the 5% level of significance. If that comparison is successful, then the same endpoint will be tested for the RPC1063 0.5 mg group vs. the IFN  $\beta$ -1a group comparison at the 5% level of significance. This procedure (Figure 2A) will continue down the rank ordered key secondary endpoint list until a comparison fails to reach statistical significance,

For the 3rd key secondary endpoint of time to onset of sustained disability progression, the data from this study will also be pooled with the data from another phase 3 study, RPC01-301, for hypothesis testing. This pooling will be described in a separate pooling plan.

If only 1 RPC1063 dose is significant on the primary endpoint, then on the rank ordered key secondary endpoint list for the surviving dose only, at the 2.5% level of significance for each key secondary endpoint (Figure 2B).

Figure 2.

Other secondary endpoint analyses will not include adjustments made for multiple comparisons and multiple endpoints.

Unless specified otherwise, all statistical analyses will be performed using a two-sided hypothesis test at the overall 5% level of significance. All p-values will be rounded to four decimal places. If a p-value is less than 0.0001, it will be reported as "<0.0001". If a p-value is greater than 0.9999, it will be reported as ">0.9999".

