### 5.1. Sample Size

Approximately 1200 patients with RMS will be randomized in this study (approximately 400 per treatment group). The primary analyses will compare the ARRs in each of the RPC1063 groups to the IFN  $\beta$ -1a group using a Poisson regression model at the alpha = 0.025 level. The control ARR is assumed to be equal to 0.3 (Mikol, 2008). Assuming extra-Poisson variation ( $\sigma^2$ =1.3) (Polman, 2011) and at least 12 months of follow-up per patient, the method of Nicholas (Nicholas, 2011) results in a total sample size of 1059 patients (353 per arm) in order to provide 80% power to detect a 43% reduction in the ARR (i.e., an ARR of 0.17 for RPC1063). To account for an assumed dropout rate of approximately 12%, approximately 1200 patients (400 per treatment group) will be enrolled.

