#### 9.1.2. Sensitivity Analysis

Two sensitivity analyses will be performed. The first sensitivity analysis will repeat the primary analysis counting both confirmed and unconfirmed relapses.

The second sensitivity analysis will use a negative binomial regression model, instead of the Poisson regression model, to compare relapse rates. The same covariates and offset term will be used as specified in the primary analysis. This model will be run twice: once repeating the primary analysis (confirmed relapses only) and once repeating the first sensitivity analysis (confirmed + unconfirmed relapses).

In addition to the specified sensitivity analyses, a Kaplan-Meier analysis on the difference in time to first confirmed relapse curves will also be performed. The estimated median time to first confirmed relapse will be reported, along with the associated 95% CI and log-rank p-values. A Kaplan-Meier plot will also be produced.

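### The Part B primary Poisson model has no allowance for overdispersion, so at the plan's own dispersion of 1.3 each dose is tested at about 0.049, not 0.025

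*SAP*

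**What the plan says.** **Primary model.** SAP section 9.1.1: "The primary analysis of ARR will be performed using a Poisson regression model". It adjusts for region, baseline age and baseline GdE lesion count, and "will include the natural log transformation of time on study as an offset term". Protocol section 13.6.4, Part B, agrees: "The primary analysis for the ARR will be carried out using a Poisson regression model", with the same covariates and no mention of the offset. Neither document says how the variance is to be estimated.

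**Error rate.** SAP section 5: "each of the 2 treatment comparisons will be tested at the alpha = 0.025 level". The same section makes tests two-sided by default. The number of doses that succeed decides whether the key secondary endpoints are tested on both doses at 5% or on one dose at 2.5%.

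**Sizing.** SAP section 5.1 begins its calculation with "Assuming extra-Poisson variation", set at 1.3. Protocol section 13.2 uses the same value.

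**Overdispersion.** For relapses it is handled only in SAP section 9.1.2: "The second sensitivity analysis will use a negative binomial regression model, instead of the Poisson regression model, to compare relapse rates". No rule lets that result replace the primary one.

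**The concern.** The sizing and the test do not match. The sizing takes the variance of the relapse count as 1.3 times its mean. An ordinary Poisson regression takes it as equal to the mean. If the sizing assumption is right, the model standard error is too small by √1.3 = 1.14 and the test rejects too often.

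The primary p-values, the rate-ratio intervals and the gate to the key secondary endpoints all rest on that standard error. The 0.025 split is there to hold the family-wise error at 5% over two doses, and this omission undoes it. The subgroup analyses and the first sensitivity analysis repeat the same model and inherit the problem.

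**Working it through.** **Inputs.** Two-sided alpha 0.025 per dose (SAP section 5). Control ARR 0.3 and dispersion φ = 1.3 (both documents). Protocol section 13.2: ARR 0.19 on RPC1063, 24 months, 90% power, 333 per arm. SAP section 5.1: ARR 0.17, at least 12 months (taken as 1 year), 80% power, 353 per arm. Allocation is 1:1:1.

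**Step 1: reproduce the stated sizes.** With the log rate ratio,

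n per arm = φ × (z₀.₉₈₇₅ + z_power)² × [1/(λ₀T) + 1/(λ₁T)] / [ln(λ₀/λ₁)]²

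- Protocol: 1.3 × (2.2414 + 1.2816)² × (1/0.60 + 1/0.38) / [ln(0.30/0.19)]² = 332.4, which rounds up to the stated 333. With φ = 1 it is 256.
- SAP: 1.3 × (2.2414 + 0.8416)² × (1/0.30 + 1/0.17) / [ln(0.30/0.17)]² = 353.0, as stated. With φ = 1 it is 272.

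Both sizes therefore assume a test whose variance is inflated by 1.3.

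**Step 2: true error of the unscaled test.** If the variance is φ times the mean but the model assumes φ = 1, the Wald statistic under no effect has standard deviation √φ.

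- Per dose: 2 × [1 − Φ(2.2414/√1.3)] = 2 × [1 − Φ(1.966)] = 0.0493.
- Family-wise, two doses sharing one control (correlation 0.5, bivariate normal): 0.0896, against 0.0465 when φ = 1.
- Coverage of a nominal 95% interval: 1 − 2 × [1 − Φ(1.96/√1.3)] = 0.914.
- Nominal p-value needed for a true 0.025: 2 × [1 − Φ(2.2414 × √1.3)] = about 0.0106.

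**Step 3: simulation under no effect.** Negative binomial counts were drawn with variance 1.3 times the mean.

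- ARR 0.30, 24 months, 333 or 400 per arm, 40,000 trials: plain Poisson gave 0.048–0.051 per contrast and 0.088–0.091 family-wise. A Pearson scale gave 0.024–0.026 and 0.046–0.048.
- A separate simulation, with mean counts of 0.3 or 0.6, gave 0.047–0.049 per contrast for plain Poisson and about 0.025 with the Pearson scale.

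**Step 4: other values of the residual dispersion.**

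| Residual φ | Per dose | Family-wise |
|---|---|---|
| 1.0 | 0.025 | 0.0465 |
| 1.075 | 0.031 | 0.057 |
| 1.1 | 0.033 | 0.060 |
| 1.15 | 0.037 | 0.067 |
| 1.225 | 0.043 | 0.078 |
| 1.3 | 0.049 | 0.090 |
| 1.5 | 0.067 | 0.12 |

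The rows at 1.225, 1.15 and 1.075 correspond to covariates removing a quarter, a half and three quarters of the 0.3 excess.

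**The case against.** **The plan is silent rather than wrong.** Neither document says the scale is fixed at 1, and the stated sizes fit an intended scaled test whose option was never written down. That may be what was meant. But a Poisson regression run as written fixes the dispersion at 1, and nothing in the plan prevents that. If scaling is intended, it has to be stated before unblinding.

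**The 0.049 is conditional.** This stands. It requires a residual dispersion of 1.3 after adjustment for region, age and baseline GdE count, and the documents do not say whether 1.3 is before or after adjustment. Covariates could absorb part of the excess, and the true value could also be higher. The source of 1.3 cannot be traced either: the citation year matches a diagnostic-criteria paper in the protocol's reference list and nothing in the SAP's. The error is nominal only if no overdispersion remains, which is not what the trial was sized for.

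**A negative binomial analysis is already planned.** It uses the same covariates and offset, on confirmed relapses and on all relapses, so it would expose a fragile Poisson result. It would not control the error rate of the confirmatory test, because it does not carry the decision. The key secondary lesion counts already use negative binomial regression as their main model.

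**The power statement must cover both documents.** This is fair, since the protocol and SAP size for different powers and effects. Both sets of inputs are covered under the fix.

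**Conclusion.** The concern holds. Run as specified, the primary test omits the variance inflation for which the trial was sized. At dispersion 1.3 the error is 0.0493 per dose against 0.025, and about 0.090 family-wise against 0.0465. The per-dose figure is the same under either sizing scenario, since both use dispersion 1.3 and alpha 0.025.

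The result rests on three assumptions: the residual variance ratio is 1.3, the model is fitted without a scale or robust variance, and the normal approximation holds, which the simulations support. The inflation shrinks if covariates absorb dispersion and grows if the true value exceeds 1.3. For a confirmatory phase 3 primary analysis this should be corrected before database lock.

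**What to change.** In SAP section 9.1.1, protocol section 13.6.4 and the protocol synopsis, name one overdispersion-robust primary analysis:

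- the same Poisson model with standard errors scaled by Pearson chi-square over its degrees of freedom, which matches the sizing most directly, or with a sandwich variance; or
- the negative binomial model of SAP section 9.1.2, promoted to primary.

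Keep the unscaled Poisson model as a sensitivity analysis. Carry the chosen method into the subgroup analyses and the analysis that adds unconfirmed relapses. As a separate reporting point, give 97.5% intervals for the two primary contrasts, so that they match tests at 0.025.

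**Cost.** Wording in both documents and one model option. The sample size does not change. With a Pearson scale, power is 90.1% at 333 per arm on the protocol's inputs and 80.0% at 353 per arm on the SAP's. With the negative binomial model it is about 92% and 83%, because constant negative binomial dispersion implies a variance ratio below 1.3 in the lower-rate arm (about 1.19 at ARR 0.19 over 24 months). Power for the sandwich variance was not computed.

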Continuous data will be presented using descriptive statistics: n, mean, standard deviation (SD), median, minimum and maximum. Categorical data will be summarized by the number and percent. Confidence intervals (CIs) will be 95% and two-sided, unless otherwise stated. Data will be displayed in all listings sorted by treatment group and subject number. When count data are presented, the percent will be suppressed when the count is zero in order to draw attention to the non-zero counts. A row denoted "Missing" will be included in count tabulations where necessary to account for dropouts and missing values. The denominator for all percentages will be the number of patients in that treatment within the population of interest, unless otherwise stated. Non-zero percentages will be rounded to one decimal place, except 100% will be displayed without any decimal places. Additional rounding rules are as follows:

- If the original value has 0 decimal places: mean, median, and CIs will have one decimal place and SD will have 2 decimal places
- If the original value has 1 decimal place: mean, median, and CIs will have 2 decimal places and SD will have 3 decimal places
- If the original value has 2 or more decimal places: mean, median, CIs, and SD will all have 3 decimal places

Minimum and maximum will always have the same decimal places as the original measure, up to a maximum of 3 decimal places.

Subgroup analysis will be performed for the primary and secondary efficacy endpoints where applicable. The following are the pre-defined subgroups:

- Baseline EDSS score (EDSS  $\leq$  3.5 vs. EDSS > 3.5)
- Baseline presence of Gd-enhancing lesions (present vs. absent)
- Prior treatment status (treatment naïve vs. previously treated)
- age at Baseline (age  $\leq 40$  vs. age > 40)
- sex (female vs. male)
- race (white vs. non-white)
- weight (< median vs.  $\ge$  median)

- number of relapses in the past 12 months ( $< 2, \ge 2$ ) for ARR endpoint only
- regions (North America, Western Europe, Eastern Europe)

Any subgroup that does not have at least 5% of the overall sample size (approximately 60 patients) will not be included in subgroup analyses.

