## 5.2. Randomization, Stratification, and Blinding

Patients will be randomized 1:1:1 to receive IFN  $\beta$ -1a 30  $\mu$ g QW, RPC1063 0.5 mg QD, or RPC1063 1 mg QD. The randomization will be stratified by Baseline EDSS category ( $\leq$  3.5, > 3.5) and country.

The randomization will be based on a stratified blocked algorithm and will be done centrally by using an Interactive Voice Response System (IVRS).

A "dual assessor" approach will be used to evaluate efficacy and safety to prevent potential unblinding as result of observed efficacy, adverse events (AEs), or laboratory changes. Separate treating and examining investigators will be designated at each center prior to randomization. Patients will be instructed to not disclose symptoms related to their treatment regimen to the blinded evaluator (examining investigator). The blinded evaluator should communicate with patients only as needed to complete the neurological examinations.

In the event that the blinding needs to be broken because of a medical emergency, the Medical Monitor should be contacted immediately. The treatment assignment will be unblinded through the IVRS. Reasons for treatment unblinding must be clearly explained and justified in the eCRF. The date on which the code was broken together with the identity of the person responsible must also be documented.

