### 7.2.2. Multiple Sclerosis Disease History

Multiple sclerosis disease history will be summarized for the ITT population using the descriptive statistics for the following parameters:

- EDSS score at Baseline
- EDSS category at Baseline
- Age at MS symptoms onset
- Age at MS diagnosis
- Years since MS symptoms onset
- Years category since MS symptoms onset
- Years since MS diagnosis
- Years category since MS diagnosis

- Number of relapses within the last 12 months prior to screening
- Number of relapses within the last 24 months prior to screening
- Number of GdE lesions at Baseline
- T2 lesion volume at Baseline

In addition to reporting the summary statistics, the following duration categories will be used for selected continuous parameters: For the years since MS symptom onset and years since MS diagnosis: 0 - <1, 1 - <2, 2 - <5, 5 - <10, 10 - <15,  $\ge 15$ . EDSS score at Baseline: 0 - 2, 2.5 - 3.5, 4 - 5, >5. Number of relapses within the past 12 and 24 months: 0, 1, 2-3, >4. Number of GdE lesions at Baseline: 0, 1, 2, 3, >4.

MS history data will be presented in a listing. Incomplete diagnosis dates will be imputed as detailed in Appendix A.

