#### 9.2.1. Analysis

# **Key Secondary Endpoint: The number of new or enlarging hyperintense T2-weighted brain MRI lesions over 24 months**

The primary analysis of the number of new or enlarging T2 hyperintense lesions over 24 months will be performed using a negative binomial regression model adjusted for region, age at Baseline, and Baseline number of GdE lesions, and will include the natural log transformation of the number of available MRI scans as an offset term. The odds ratios and their associated 95% CIs, relative reductions, and p-values will be reported.

The analysis will be repeated in each of the pre-specified subgroups shown in section 5. Forest plots showing the odds ratios and 95% CIs for the overall result and the results in each subgroup will be constructed.

Three sensitivity analyses will be performed: the first will repeat the primary T2 analysis using the mean number of T2 lesions from patients from the same treatment group to impute missing T2 values. The second will repeat the primary T2 analysis using last observation carried forward (LOCF) method for imputing missing T2 data values. Only data from post-Baseline MRI scans can be carried forward to subsequent timepoints for this analysis. The third will repeat the primary T2 analysis using only patients with complete T2 data at the relevant MRI visits (observed cases analysis). All three sensitivity analyses will include the natural log transformation of exposure time on study (instead of the number of available MRI scans) as the offset term.

All T2 lesion results will be listed.

#### Key Secondary Endpoint: The number of GdE brain MRI lesions at Month 24

The number of GdE brain MRI lesions at Month 24 will be analyzed using a negative binomial regression model adjusted for region, age at Baseline, and Baseline number of GdE lesions, and will include the natural log transformation of the number of available MRI scans as an offset term. The odds ratios and their associated 95% CIs, relative reductions, and p-values will be reported.

The analysis will be repeated in each of the pre-specified subgroups shown in section 5. Forest plots showing the odds ratios and 95% CIs for the overall result and the results in each subgroup will be constructed.

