#### Analysis Method

All disability progressions will be identified as confirmed after 3 months, confirmed after 6 months, or unconfirmed prior to database lock. The primary analysis of time to disability progression will be analyzed by a Cox proportional hazards model with factors

for treatment group, adjusted for region, age at Baseline and Baseline EDSS score. Handling of ties will be according to Efron. The hazard ratio, associated 95% CI, and p-values will be reported.

A Kaplan-Meier analysis on the difference in time to disability progression curves will also be performed. The estimated median time to disability progression will be reported, along with the associated 95% CI and log-rank p-values. A Kaplan-Meier plot will also be produced.

Each of these analyses will be performed on disability progressions confirmed after 3 months and again on disability progressions confirmed after 6 months.

Sensitivity analyses will be performed and include the following:

- Counting patients with a Baseline EDSS = 0 as a progression only if the EDSS score increases by at least 1.5 points
- Including unconfirmed progressions in each analysis
- Counting premature study discontinuations as confirmed progressions in each analysis
- Including unconfirmed progressions and counting premature discontinuations as progressions in each analysis

All disability progressions will be listed.

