### 9.3.1. Analysis

Secondary Endpoints: The proportion of patients who are GdE lesion-free at Month 24, and the proportion of patients who are T2 lesion-free at Month 24

Each of these endpoints will be analyzed using a Cochran-Mantel-Haenszel (CMH) test

stratified by region and EDSS category at Baseline. The numbers and percentages of patients with 0, 1-2, 3-4, and  $\geq$  5 lesions will be reported. The proportion of patients who are lesion-free will be reported along with the associated 95% CI. The difference in proportions between each RPC1063 group and the IFN  $\beta$ -1a group will also be reported with the associated 95% CI and CMH p-value. Patients who are missing the Month 24 MRI data will be considered non-responders, i.e., as not being lesion-free.

Sensitivity analyses will be conducted using the LOCF method for replacing missing Month 24 MRI data and on the subset of patients with non-missing Month 24 MRI data (observed cases analysis).

Secondary Endpoint: Change in normalized brain volume (atrophy) on MRI scans from Baseline to Month 24

Brain volumes will be reported in cm^3. If the data are collected in mm^3, then a transformation will be applied by dividing the result in mm^3 by 1000 to convert to cm^3 prior to analysis.

Actual brain volumes, change from Baseline to each visit, and percent change from Baseline to each visit will be summarized. Comparisons of the change and percent changes between the treatment groups will be analyzed using an analysis of covariance (ANCOVA) model adjusted for region, EDSS category at Baseline, and brain volume at Baseline. The mean difference between each RPC1063 treatment group and IFN  $\beta$ -1a will be reported with the associated 95% CI and p-value. Patients with missing data will have their results imputed via LOCF.

Secondary Endpoint: Change in MSFC score from Baseline to Month 24 (including the low-contrast letter acuity test [LCLA] measurement of visual function as a component)

The MSFC score is a battery of the following 3 individual scales:

- The Timed 25-Foot Walk is a quantitative measure of lower extremity function
- The 9-Hole Peg Test is a quantitative measure of upper extremity (arm and hand) function
- The Symbol Digit Modalities Test (SDMT) is a measure of cognitive impairment that assesses attention, visuoperceptual processing, working memory, and psychomotor speed

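### The relapse, T2 and GdE count models leave out baseline EDSS, a randomisation stratum that the SAP's other adjusted efficacy models use; the relapse model also leaves out pre-study relapse count

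*SAP*

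**What the plan says.** **Randomisation.** SAP 5.2: "The randomization will be stratified by Baseline EDSS category" (≤3.5, >3.5) and by country. Protocol 13.4 agrees.

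**Primary relapse model.** SAP 9.1.1: "The model will compare treatment groups, adjusted for region, age at Baseline, and the Baseline number of GdE lesions", with log time on study as offset. The protocol synopsis and 13.6.4 give the same covariates.

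**T2 and GdE key secondary endpoints.** SAP 9.2.1 specifies for each a "negative binomial regression model adjusted for region, age at Baseline, and Baseline number of GdE lesions". The protocol again agrees.

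**Relapse sensitivity models.** SAP 9.1.2: "The same covariates and offset term will be used as specified in the primary analysis".

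**Other adjusted efficacy models.** The lesion-free proportions use a CMH test "stratified by region and EDSS category at Baseline" (SAP 9.3.1; also protocol 13.6.4). The disability Cox model is "adjusted for region, age at Baseline and Baseline EDSS score" (SAP 9.2.1), so it uses the score and not the category. The ANCOVAs for brain volume, MSFC, LCLA and MSQOL-54 in SAP 9.3.1 adjust for EDSS category; for these the protocol has age instead.

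**Prior relapses.** SAP 7.2.2 summarises "Number of relapses within the last 12 months prior to screening". SAP 5 lists "number of relapses in the past 12 months" (<2, ≥2) as a subgroup for the ARR endpoint alone. It is a covariate in no visible model.

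**The concern.** A factor used to balance the randomisation is normally carried into the analysis. Here it is missing from the primary endpoint and the two highest-ranked key secondary endpoints, and present further down. The contrast is sharpest in the MRI data: T2 and GdE lesions are analysed with EDSS strata as lesion-free proportions, but without EDSS as counts, which rank higher. Neither document gives a reason. No planned analysis fills the gap, because the relapse sensitivity models inherit the primary covariates and subgroup runs do not adjust the overall estimate.

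What is at stake is precision. If EDSS predicts the outcome, stratified allocation has already removed some chance imbalance, and a model that ignores the stratum reports a standard error slightly too large. The test is then conservative and loses some power. T2 opens the key secondary sequence, which stops at the first failure, so precision lost there can block the endpoints below it.

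**Working it through.** **1. Reproduce the stated sample sizes.** With n per arm = (z₁₋α/₂ + z_power)² × φ × [1/(λ₀t) + 1/(λ₁t)] / [ln(λ₁/λ₀)]², two-sided α = 0.025 and extra-Poisson variation φ = 1.3:

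- SAP 5.1 (0.30 vs 0.17, 12 months, 80% power): 9.505 × 1.3 × 9.216 / 0.3226 = 352.98, so **353**, as stated.
- Protocol 13.2 (0.30 vs 0.19, 24 months, 90% power): 12.411 × 1.3 × 4.298 / 0.2086 = 332.4, so **333**, as stated.

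Neither uses a covariate, so planned power does not depend on the omitted factors.

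**2. Assumptions.** The documents give no prognostic strength. Assumed: 20% of patients with EDSS >3.5, 30% with ≥2 prior relapses, and rate ratios (RR) of 1.0, 1.3, 1.6 or 2.0 for each factor, conditional on region, age and baseline GdE count. Control-arm variance/mean is held at 1.3, so total between-patient variance is v_tot = 0.3/0.3 = 1.0 at 12 months and 0.3/0.6 = 0.5 at 24 months.

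**3. Relapse model, by hand.** A binary factor contributes v = p(1−p)(RR−1)² / (1+p(RR−1))². At RR 2.0, v = 0.16/1.44 = 0.111 for EDSS and 0.21/1.69 = 0.124 for prior relapses. Residual variance is (1+v_tot)/[(1+v_E)(1+v_R)] − 1. A Pearson scale averages about 1 + variance × mean count over both arms; the mean counts are (0.30+0.17)/2 = 0.235 and (0.60+0.38)/2 = 0.49.

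- SAP sizing, RR 2.0: residual = 2/(1.111×1.124) − 1 = 0.601. The scale falls from 1.235 to 1 + 0.601×0.235 = 1.141, and the SE by 1 − √(1.141/1.235) = 3.9%.
- Protocol sizing, RR 2.0: residual = 1.5/(1.111×1.124) − 1 = 0.201. The scale falls from 1.245 to 1 + 0.201×0.49 = 1.098, and the SE by 1 − √(1.098/1.245) = 6.1%.

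**4. Relapse model, simulated.** 10,000 two-arm gamma-Poisson trials per scenario, EDSS balanced across arms, with and without both covariates:

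| Assumed RR | 1.0 | 1.3 | 1.6 | 2.0 |
|---|---|---|---|---|
| SAP sizing: fall in scaled SE | 0.1% | 0.6% | 1.8% | 3.8% |
| SAP sizing: power change, points | +0.1 | +0.4 | +1.3 | +2.4 |
| Protocol sizing: fall in scaled SE | 0% | 0.8% | 2.7% | 6.0% |
| Protocol sizing: power change, points | −0.2 | +0.4 | +0.9 | +2.2 |
| Scaled size without covariates (SAP sizing) | 0.027 | 0.024 | 0.022 | 0.022 |
| Unscaled size without covariates (SAP sizing) | 0.048 | 0.047 | 0.045 | 0.044 |
| Unscaled size with covariates (SAP sizing) | 0.047 | 0.046 | 0.045 | 0.041 |

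The unscaled Poisson SE is 0.163 (SAP sizing) or 0.114 (protocol sizing) with or without the covariates. Unscaled power under SAP sizing is 0.89 throughout, but at a true size well above 0.025. That excess comes from overdispersion: in closed form, 2[1 − Φ(2.2414/√1.3)] = 0.049. The covariates barely touch it.

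**5. MRI models.** 600 negative binomial trials per scenario, 400 per arm, adding EDSS category only. Assumed: 15–25% with EDSS >3.5; T2 control mean 5, dispersion 0.5–2, 40% reduction; GdE control mean 0.4, dispersion 2–4, 50% reduction. Patients per arm = 400 × (1 − SE ratio²), from unrounded ratios.

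| Assumed RR | 1.0 | 1.3 | 1.6 | 2.0 |
|---|---|---|---|---|
| T2: fall in SE | 0.1% | 0.3–0.9% | 0.8–2.8% | 1.7–6.0% |
| T2: worth, patients per arm | 0 | 2–7 | 6–22 | 14–46 |
| GdE: fall in SE | 0.1% | 0.2% | 0.4–0.5% | 0.8–1.1% |

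**The case against.** The primary test as written gains nothing: the unscaled Poisson SE does not move. Every prognostic input is assumed, and at a rate ratio of 1.3 the scaled relapse power gain is 0.4 points. The figure of 46 patients per arm for T2 needs the strongest effect, the lowest dispersion and the largest EDSS share together. Covariates may also reasonably differ by endpoint: a CMH test needs categorical strata, baseline EDSS is the endpoint's own baseline in the Cox model, and the lesion models already adjust for baseline MRI activity. Protocol and SAP agree, so the choice is pre-specified. Country, the other stratum, appears only as region throughout. Prior relapse count is not a stratum.

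Most of this stands as a limit on size. The point is one of efficiency, and prior relapse count is the weaker of the two additions. The need for categories explains the form of the CMH strata. It does not explain why a randomisation stratum is absent from count models that could take it at the cost of one parameter. Agreement between the documents rules out a contradiction but supplies no reason. Exploratory analyses are not visible and could not be checked.

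**Conclusion.** The concern holds as an efficiency and consistency gap. It creates no bias, type I error inflation or protocol–SAP conflict, and the stated sample sizes stand. Under the assumed rate ratios, the gain in relapse power with a variance that allows for overdispersion runs from nil to about 2.4 points. T2 has the largest possible gain among the MRI models, and GdE very little. The range includes zero if neither factor is prognostic, and would be exceeded if they are stronger than assumed. The benefit falls on the two MRI models, the planned negative binomial relapse analysis, and any primary relapse model whose variance allows for overdispersion. The change should be made because it costs almost nothing and the omission has no stated reason.

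**What to change.** Before unblinding, amend SAP 9.1.1 and 9.2.1 and the protocol synopsis and 13.6.4:

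1. Add baseline EDSS category (≤3.5, >3.5) to the relapse, T2 and GdE models. State whether the stratum recorded at randomisation or the baseline value is used.
2. Add relapses in the prior 12 months to the relapse model, in the form already used for the subgroup (<2, ≥2).
3. Give a missing-data rule for that count that does not depend on treatment arm, for example the pooled most frequent category.
4. In subgroup runs, drop the covariate that defines the subgroup.

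The negative binomial relapse sensitivity analysis then inherits the covariates. Region can remain as the stand-in for country. If the sponsor prefers to keep the present models, the lesser step is a pre-specified sensitivity analysis with these covariates, or a stated reason for leaving them out.

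The cost is wording, one extra parameter in each MRI model and two in the relapse model. If neither factor is prognostic, SEs change by 0.1% or less. This does not replace a scale term, robust variance or negative binomial primary model for the relapse endpoint.
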